provided can be found in the attachment to this section. The final product was already submitted to the IRB and should be on file.) Participants will be called on Day 14 to see if they received the shipment (if not a second shipment can be mailed), to answer any questions, and to encourage use of the informational resources provided as part of this study; this check-in should not last more than 3-5 minutes. After the Day 0 survey, whether it's done via phone or mail, participants in the SS+NRT group will receive the same consultation about free or low-cost resources related to their two most pressing unmet social support needs. In this same call, participants will receive brief advice related to smoking cessation (10-15 minutes). Consistent with the brief advice model described in the latest Clinical Practice Guideline for Treating Tobacco Use and Dependence (CPG-TTUD; Fiore et al., 2008), participants will be informed about the general health benefits of smoking cessation, given an overview of evidence-based approaches to smoking cessation (e.g., stimulus control, medication use, support seeking), and provided with a summary of the mechanism of action and potential benefits/risks of NRT specifically. They will be encouraged to try NRT in the context of a "practice" quit attempt, even if the abstinence they achieve only lasts a few hours. There will not be any pressure to achieve long-term success during the course of study participation, but participants will be told that multiple "practice" quit attempts could result in 1) learning which approaches and coping strategies do vs. do not work for them and 2) increasing their motivation/confidence in their ability to quit for good. It should also be noted that participants will be assured there is no requirement to quit, reduce smoking, or even try NRT as part of this study. The goal of this study is to encourage a "hassle-free" quit attempt. After the consultation, and in the same mailing as the social support resource directory, a free 2-week supply of nicotine patches (14mg; NicoDerm CQ - GlaxoSmithKline) and nicotine lozenge (2 or 4mg; Nicorette - GlaxoSmithKline) will be supplied; participants will be forewarned about the NRT shipment via the US Postal Service metered mail, and given the opportunity to opt out if they like. As for the amount of NRT, each participant who doesn't opt out of the shipment will be mailed one box of 14 nicotine patches (1 patch per day) and one box of 72 nicotine lozenges (2mg or 4mg supply based on time to first cigarette as per the package label, with 1 lozenge per 1-2 hours when awake) in their original packaging. A summary of the information discussed on the phone will be provided. Participants will be called on Day 14 to see if they received the shipment (if not a second shipment can be mailed), to answer any questions, and to encourage use of the informational and medication resources provided as part of this study; again, this check-in should not last more than 3-5 minutes. Participants in both groups will be asked to complete a Day 30 and 60 survey (see Data Collection attachment). Finally, on or shortly after Day 74, all participants will receive a final letter that briefly outlines the importance and benefits of smoking cessation for cancer survivors and provides up-to-date contact information and the latest flyer for the KY Quitline (see attachment in this section). It should be noted that women of childbearing potential will be asked to take a pregnancy exam before consenting to take part in this study because pregnancy is an exclusionary criterion; this is something they will need to do on their own. If participants of childbearing age are assigned to the SS+NRT group, they will be also asked to engage in an effective method of birth control (e.g., abstinence from sex, oral contraceptive, intrauterine contraceptive device) during study participation. Finally, if a woman becomes pregnant during this study, they will be asked to immediately inform the PI who will then have [name], the Medical Supervisor for this study, contact them and advise them on stopping NRT, if appropriate. No information will be entered into participants' EHR as part of this study.

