The primary protection against the physical risks associated with both nicotine patch and nicotine lozenge (both over-the-counter medications) is that it will only be provided for a short duration and smokers with FDA contraindications will not be enrolled in this study. Second, the Data and Safety Monitoring Plan (DSMP) includes AE monitoring, and the PI, RAs, and Medical Supervisor ([name]) will work closely together to make sure that participants' AEs are handled in a timely and responsible manner. Third, females of childbearing potential will be asked to use effective contraception to guard against pregnancy during the course of the study (this is on top of exclusion criteria related to pregnancy/breastfeeding). Fourth, participants will be encouraged to contact the PI and stop the use of the nicotine patch and consult with their physician or advanced practice registered nurse as instructed on the package insert. Finally, participants who report a serious AE will be withdrawn from the study. Several steps will be taken to minimize psychological risks. First, participants will be alerted to the possibility of mild emotional discomfort prior to their enrollment in the study, as the consent form will provide information about the nature of the surveys. Second, participants will be assured via the consent form and verbal assurances from the PI and RAs that their data are confidential. Third, participants will be allowed to skip any question or withdraw from the study at any time. Finally, participants who experience emotional discomfort as a result of this study will be: 1) allowed to withdraw from the study without penalty and 2) provided with contact information for mental health professionals near their place of residence. Note that as a licensed clinical psychologist in Kentucky, the PI has access to a list of licensed psychologists and related mental health professionals who practice throughout the state, and can provide said information to anyone who requests it. To address confidentiality risks, well-established guidelines for security best practices will be followed, with particular attention to guidelines for data collected electronically. Although not specific to this study, both KCR and UK HealthCare have established safety precautions: 1) KCR has an established means of encrypted electronic file transfer that involves unique username and password authentication, and will only release participant data through that avenue and 2) UK HealthCare Enterprise has an established means of training everyone prior to granting them access to one or more of their EHR systems, and once access is given, an audit trail is created via the requirement of unique username and password authentication prior to each log-in. The safety precautions specific to this study are as follows: First, the responses of any one participant will never be reported apart from those of other participants. Second, all participants will be assigned a unique identification number. Only participants' unique identification number will identify their survey data. Within a month of receiving participants' health information from KCR, these data will be coded such that only participants' unique identification number is associated with their health information (e.g., if names are used to identify cases in the file given to me by the registry, then the names will be removed and replaced with participants' unique identification number). In this way, only participants' unique identification number will identify their sensitive health information and survey data. Third, the electronic document that links participants' unique identification number with their private individually identifiable information (i.e., name, address, phone number) will be strictly protected (only the PI and RAs will have access), password protected, and stored on a secure server maintained by the UK College of Arts & Sciences. Fourth, the electronic document that contains a list of patients to be screened will be strictly protected (only the PI and RAs will have access), password protected, and stored on a secure server maintained by the UK College of Arts & Sciences. Fifth, this study will use UK computers that will: 1) be protected from access by outside parties through the use of a firewall, 2) be password protected, 3) have regular backups performed, and 4) have operating system patches and antivirus software kept up-to-date. These computers will be physically housed on the 2nd and 3rd floor of the UK Combs Cancer Research Building and the basement and 2nd floor of UK Kastle Hall, as the PI's office and lab space is spread across these two buildings. Sixth, access to electronic study files will be restricted to the PI and select RAs, and all individuals who are granted access will need to pass through username and password authentication as these files will be stored on the College of Arts & Sciences secure server. Similarly, access to paper study files will be restricted to key study personnel, as these files will be kept in lockable filing cabinets that are stored on the basement floor of the Kastle Hall behind locked doors. Seventh, the surveys will be administered with the use of Research Electronic Data Capture (REDCap) whenever they are done by phone, and whenever they are done by paper, participants' responses will then be entered into REDCap. REDCap is designed to provide a secure, reliable, and valid means of electronic data capture as it will: 1) operate behind a firewall on a secure UK server, 2) minimize data entry errors via automatic data validation, 3) provide a "real time" searchable log of input and output, and 4) allow the creation of audit trails. Seventh, any transfer of electronic files between the PI and KCR will be completed using their established means of encrypted file transfer that involves unique username and password authentication. Finally, all study personnel will maintain up-to-date human subjects protection training. It should also be noted that we will not retain beyond the anticipated end of the study (07/31/20) the name or contact information (i.e., phone number and mailing address) for cancer survivors who "opt in" to KCR's releasing this info to the PI, but ultimately do not enroll in the study. Additionally, we will not retain beyond the aforesaid date the list of patients to be screened as part of the clinic-based recruitment. That is, unless someone provides written informed consent to study participation, we will not keep a record of his or her personal information. This personal information will be destroyed according to UK Policy A13-050. Financial Risks: These risks will be explained to potential participants as part of the informed consent process and will be offset by the financial compensation participants will receive.

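### The stop-use step in Safety Precautions names only the nicotine patch, although patch and lozenge are mailed together

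*Combined protocol and SAP*

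**What the plan says.** Safety Precautions (Research Description) opens its physical-risk list with "The primary protection against the physical risks associated with both nicotine patch and nicotine lozenge", so the list is meant to cover both products. The first item is the short supply together with exclusion of smokers who have FDA contraindications. The second is adverse-event monitoring, in which the PI, research assistants and Medical Supervisor work together so that "participants' AEs are handled in a timely and responsible manner". The third is contraception. The fourth is the stop-use step: participants are asked to get in touch with the PI, and the advice then reads "stop the use of the nicotine patch and consult with their physician or advanced practice registered nurse as instructed on the package insert". The last is that "participants who report a serious AE will be withdrawn from the study".

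Research Procedures describes the supply. Each SS+NRT participant who does not opt out is sent "one box of 14 nicotine patches (1 patch per day) and one box of 72 nicotine lozenges", in original packaging. The same section gives the only other stop instruction, for a participant who becomes pregnant: the Medical Supervisor is to contact her and "advise them on stopping NRT, if appropriate".

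Potential Risks attributes mouth and throat soreness and hiccups to the lozenge, and nausea to both products. Study Drug Information lists two separate package inserts, one for each product.

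**The concern.** A safety instruction should cover every product that the trial supplies. Read literally, this one tells a participant whose problem comes from the lozenge to stop the patch, and says nothing about the lozenge. It also refers to one package insert where two products, each with its own insert, are in the mailing.

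What is at stake is the completeness of advice to participants who manage the medication at home, since treatment is delivered by phone and mail. The lozenge's expected local effects include soreness of the mouth and throat, and the sample includes head/neck cancer survivors. That gives a clinical reason for the wording to be right, although the eligibility table is an attachment outside the reviewed text and may screen out some of those at risk. No endpoint, sample size or analysis is affected.

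**Working it through.** This is a check of wording. The plan gives no figure to reproduce, and the only arithmetic is a count.

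**Products and stop instructions, side by side**

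| Item | Where | Products covered |
|---|---|---|
| Introduction to the physical-risk list | Safety Precautions | Patch and lozenge |
| Mailing to SS+NRT | Research Procedures | Patch and lozenge |
| Common adverse events | Potential Risks | Patch and lozenge |
| Package inserts on file | Study Drug Information | One for the patch, one for the lozenge |
| General stop-use step | Safety Precautions, fourth item | Patch only |
| Stop advice in pregnancy | Research Procedures | NRT as a whole, pregnancy only |
| Serious adverse event | Safety Precautions, last item | Withdrawal from the study, no product named |

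**Step 1. Is the lozenge named in any general stop-use step?** No. The two other provisions are special cases. The pregnancy provision does cover NRT as a whole, but it does not reach a participant with a lozenge side effect. Withdrawal after a serious event does not say which product to stop and does not apply to non-serious events.

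**Step 2. Is a reason given for limiting the step to the patch?** None was found. Where the plan speaks of NRT risk elsewhere, it names both products or uses a term that covers both. The patch-only wording therefore looks like a drafting slip.

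**Step 3. How many participants could it concern?**
- Planned enrolment: 80. Allocation: 1:1.
- SS+NRT arm, if the arms are equal: 80 / 2 = 40.
- Participants mailed both products: 40 minus opt-outs. The opt-out rate is not given, so 40 is the ceiling.
- Products named in the stop-use step: 1 of 2.

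**Step 4. Are lozenge effects expected?** Yes. Of the six common adverse events in Potential Risks, three are patch only (skin irritation, headache, insomnia), two are lozenge only (mouth and throat soreness, hiccups) and one is shared (nausea). Lozenge-linked: 2 + 1 = 3 of 6. This counts labels, not events. It shows that the omitted product has expected effects of its own and does not measure how often they occur.

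**The case against.** The strongest reply is that this text is an answer in an IRB application and is not handed to participants. They receive an advice call that covers the benefits and risks of NRT, a written summary of it, a consent form, and both products in original packaging. Contacting the PI and consulting a clinician are not tied to the patch, and adverse-event handling covers all events. Use is voluntary: participants are told that "there is no requirement to quit, reduce smoking, or even try NRT as part of this study". Most of this stands, and it is why the point is minor. It does not remove the mismatch, because none of these provisions names the lozenge as a product to stop.

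A reader might infer four stronger things that the documents do not support.

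- **That participants get no stop advice for the lozenge.** The call script, mailed summary, consent form, inserts and lozenge Study Drug Attachment are outside the reviewed text and may already give it.
- **That a number of participants are left unprotected.** The adverse-event rates in Potential Risks come from earlier NRT studies, many with much longer sampling periods, and are not split by product. They cannot show how many would meet a stop condition on the lozenge label.
- **That the Day 14 call works against the precaution.** Staff are to "encourage use of the informational and medication resources provided as part of this study", but they also answer questions, and no script is available to show a conflict.
- **That a separate rule to stop both products is needed for symptoms of nicotine excess.** That symptom list includes nausea, which is also a common effect of each product, so such a rule could stop use for an ordinary mild event. Whether either insert calls for it cannot be checked here.

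**Conclusion.** The point holds as a minor scope error in a stated safety instruction. The general stop-use step names one of the two supplied products, although its own list is introduced as covering both. It concerns at most 40 of 80 participants, assuming equal arms and no opt-outs, and fewer once opt-outs are counted.

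Confidence is high for the wording, because no other section supplies a general stop step for the lozenge. The documents do not establish that anyone would be given wrong advice or come to harm, and that is not claimed. Nor do they suggest that the sponsor meant to exempt the lozenge.

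**What to change.** Amend the fourth precaution in two places. Replace the reference to the patch alone with *the nicotine patch and/or nicotine lozenge*, and replace the reference to a single insert with *each product's package insert*. Leave the contact with the PI and the clinician consultation as they are.

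Keep stopping tied to the labels. Do not add a blanket stop for any adverse event or a separate trigger for nicotine excess: mild expected effects should lead to stopping only where that product's insert says so. The Medical Supervisor can confirm the wording against the two inserts already on file. Then check that the participant materials (consent form, call scripts, mailed summary) agree with the amended sentence.

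The cost is a one-sentence amendment and a reading of existing materials. It adds no participants, contacts, staff or data fields, and it leaves the NRT-sampling intervention unchanged. If all NRT shipments have already been made, the edit only corrects the record.

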The demographic composition of the sample should resemble the population of cervical and head/neck cancer survivors in Kentucky, within the confines of the eligibility criteria. Regarding the racial/ethnic breakdown of the sample, most participants are expected to describe themselves as White, non-Hispanic given that recent US census data indicates that 85% of all Kentucky residents are White, non-Hispanic (<http://www.census.gov/>). Regarding the gender breakdown of the sample, it is expected that 70% of the sample will be female. This is because cervical cancer survivors in the US population tend to report a high rate of current smoking (e.g., Coups & Ostroff, 2005), a phenomenon that should result in a relatively higher enrollment rate for (female) cervical cancer survivors as opposed to (the mixed gender group of) head/neck cancer survivors. More details about the expected demographic composition of the sample may be found in the Targeted/Planned Enrollment Table attached to this section. Finally, the operationalization of "current smoker" and both "rural" and "Appalachian" residence may be found in the "Participants" section of the grant.

Attachments

Attach Type	File Name
StudyPopulation	Inclusion Criteria Table.pdf

Subject Recruitment Methods & Privacy: Using active voice, describe plans for the identification and recruitment of subjects, including how the population will be identified, and how initial contact will be made with potential subjects by those having legitimate access to the subjects' identity and the subjects' information.

Describe the setting in which an individual will be interacting with an investigator or how and where members of the research team will meet potential participants. If applicable, describe proposed outreach programs for recruiting women, minorities, or disparate populations as participants in clinical research. Describe steps taken to minimize undue influence in recruiting potential participants.

Please note: Based upon both legal and ethical concerns, the UK IRB does not approve finder's fees or "cold call" procedures made by research staff unknown to the potential participant. The ORI/IRB does not control permission to any UK listserv, mass mailing list, etc. Investigators must secure prior approval for access and use from owners/managers.

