For additional details, see topic "Recruitment of Subjects/Advertising" on ORI's [IRB Survival Handbook web page](#) and the [PI Guide to Identification and Recruitment of Human Subjects for Research \[PDF\]](#).

The PI will share responsibility for recruitment and enrollment (i.e., attainment of written informed consent) of eligible cancer survivors with the co-investigators and research assistants (RAs) who are authorized to obtain consent. Recruitment for this study involves three separate avenues: 1) a population-based approach, 2) a clinic-based approach, and 3) an individual approach. Advertising will not be performed. Population-Based: Kentucky Cancer Registry (KCR) will assist in recruitment to the extent that its staff will identify potential participants for this study. Potentially eligible cancer survivors from the perspective of the KCR will be defined as individuals who were: 1) diagnosed with cervical or head/neck cancer (e.g., larynx, oral cavity) in the past 5 years, 2) residents of a rural or Appalachian Kentucky county at the time of cancer diagnosis, 3) between 18 and 75 years old at time of cancer diagnosis, and 4) noted as having a history of tobacco use. All of these qualities are coded in KCR's database in a manner that easily allows for the identification of potential study participants for the purposes of recruitment. KCR will make initial contact with potentially eligible individuals using their established two-step procedure. Step one involves physician notification. Specifically, KCR will contact the physician of record, inform the physician of the study and the cancer survivor's potential for study participation, and then ask the physician to inform KCR if there is any reason why the cancer survivor should not be invited to participate in the study. If the physician of record indicates the cancer survivor should not be contacted, the cancer survivor will not be invited to participate in the study. All others will advance to the next step. Step two involves cancer survivor notification. Specifically, KCR will contact cancer survivors by mail to inform them of their potential for study participation. Cancer survivors will be provided a pre-addressed, postage-paid response card on which they may indicate if they do or do not want their name and contact information released to the PI. If a reply is not received within two weeks, then up to five phone calls will be made in an attempt to obtain verbal consent for the release of the cancer survivor's name and contact information. Only those cancer survivors who "opt in" to the potential for study participation will have their names and contact information (i.e., phone number and mailing address) released to the PI. Once the PI has the names and contact information (i.e., phone number and address) of people who express interest in study participation, RAs will attempt to call these individuals and screen them for eligibility. Up to five calls will be made to each person. If someone cannot be reached by phone, then 1-2 introductory letters will be mailed to the address of record (see attachment in the "Research Procedures" section). These letters will contain office phone numbers that interested individuals can use to contact the PI or RAs. Over the phone (whether the call is initiated by the research team or the cancer survivor), cancer survivors will be given a brief overview of the study procedures, have their initial questions answered, and screened for eligibility (see attachment in the "Research Procedures" section). If interested and eligible, attempts will then be made to enroll them into the study (see "Informed Consent Process" below). A few notes about the KCR: First, its recruitment procedures are not subject to modification by an individual investigator and a standardized postcard is used for notification about potential study participation; this is outside the PI's control. Second, it is not part of a "covered entity" and therefore HIPAA authorization for release of Personal Health Information, including contact information, is not required. Finally, study personnel will not have access to any identifying information for any cancer survivor until the standardized recruitment procedures described below are complete. Clinic-Based: Clinic-based recruitment focuses on recently diagnosed cancer survivors because they are unlikely to be captured in KCR's database due to the lag time between cancer diagnosis and registry entry. Here participants will be recruited through Markey Cancer Center's 1) Multidisciplinary Clinic and 2) Gynecological Oncology Clinic. On a weekly basis, [name] (Multidisciplinary Clinic – head/neck cancer care), [name] [name] (Gynecological Oncology Clinic – cervical cancer care), and/or RAs will access the UK HealthCare's electronic health record system in use in the Markey Cancer Center to review the relevant clinic schedules and identify patients presenting for an appointment related to a head/neck or cervical cancer diagnosis that occurred in the past year. If patients' healthcare provider agrees, then the PI or a RA will speak with the patient that day about the study (schedule permitting). As per the norm for the aforesaid clinics, an exam room or other private room will be used to give patients a brief overview of the study procedures and then screen them for eligibility. If interested and eligible, attempts will then be made to enroll patients into the study. If an in-person conversation is not possible the day of patients' appointment due to incompatible schedules or whatever else, then a RA will follow-up with that individual via phone within a couple of weeks. In this scenario, the same approach that is used to reach potential participants identified by KCR will be used (i.e., phone call(s) then letter(s)). Again, if individuals are found to be interested and eligible, attempts will then be made to enroll them into the study. In order to carryout this aspect of recruitment, we need to generate a list of individuals to be screened for eligibility (i.e., a list of individuals who are scheduled for an appointment related to a recent (i.e., past year) head/neck or cervical cancer diagnosis). This list will contain only this info: patients' first and last name, address, phone number, and appointment info (i.e., place, date, and time); no other PHI is needed for these individuals. This information is necessary in order to 1) have the RAs arrange their schedule so they can try to screen people in person and 2) have the RAs follow-up with someone missed in clinic. A HIPAA Waiver of Authorization is requested for this aspect of the study. Individuals: Cervical and head/neck cancer survivors in the PI's active studies (IRB #14-0599-P4S and 16-0517-P4S) who on their Consent Form answered "yes" to the question about being contacted for future studies will be contacted about this study. Once again, the same approach that is used to reach potential participants identified by KCR will be used (i.e., phone call(s) then letter(s)). And again, if individuals are found to be interested and eligible, attempts will then be made to enroll them into the study. Regardless of the avenue by which people are recruited, each individual identified as a potential participant will be assigned a unique identification number (e.g., 568, 254), and there will exist an electronic document that links each individual's name and contact info (address, and phone numbers) with their unique identification number.

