1. Accrual will be calculated as the number of participants enrolled divided by the number of individuals contacted about study participation. It will be reported as a percentage. No inferential statistical test will be conducted for this outcome. Only descriptive analyses apply.
2. Retention will be calculated as the number of assessments at the end of study divided by the number of participants enrolled. It will be reported as a percentage. No inferential statistical test will be conducted for this outcome. Only descriptive analyses apply.
3. Acceptability will be determined by the total score on the Treatment Acceptability and Preferences measure. It will be reported as a mean. An Independent samples t-test (2 sided) will be used to examine if the treatment group reports a better outcome than the control group.

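### Does reporting accrual only as enrolled over contacted leave the pilot's recruitment result hard to interpret?

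*Combined protocol and SAP*

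**What the plan says.** SAP, Outcome Measures, item 1: "Accrual will be calculated as the number of participants enrolled divided by the number of individuals contacted about study participation". The result is a percentage, analysed descriptively and without a test. Study Design names accrual and retention as the feasibility outcomes on which the pilot focuses, and sets the goal of 80 enrolled.

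Subject Recruitment Methods & Privacy: "Recruitment for this study involves three separate avenues".

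- **Registry.** The registry selects on cancer site, diagnosis in the past 5 years, rural or Appalachian residence, age, and being "noted as having a history of tobacco use". Then "KCR will make initial contact with potentially eligible individuals using their established two-step procedure". The first step goes through the doctor: "If the physician of record indicates the cancer survivor should not be contacted", that person is not invited. The second is a mailing, with up to five calls if there is no reply. Only people who opt in are passed to the study team. After that, "RAs will attempt to call these individuals and screen them for eligibility". "If someone cannot be reached by phone, then 1-2 introductory letters will be mailed to the address of record".
- **Clinic.** Patients with a head/neck or cervical diagnosis in the past year are listed. If the provider agrees, they hear an overview and are then screened. Those missed in clinic are followed up by phone and letter.
- **Individuals.** Participants in the investigator's active studies who agreed to future contact are phoned or written to, then screened.

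Study Population explains the expected 70% female share by smoking prevalence among cervical cancer survivors, "a phenomenon that should result in a relatively higher enrollment rate for (female) cervical cancer survivors".

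**The concern.** Current smoking, pregnancy and contraindications to nicotine replacement bear on enrolment, but none is stated as a filter before contact on any route. The denominator can therefore contain people who could never have enrolled. The filters also differ: the registry uses tobacco history, while none is stated for the clinic list. If the eligible share differs by route, the pooled percentage moves with the mix of routes even when willingness is constant.

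The word *contacted* adds a second uncertainty. On the registry route it could mean people written to by the registry, people called or written to by the study team, or people actually reached.

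At stake is how a later trial would use the pilot. A low yield caused by ineligibility calls for better pre-selection; one caused by reluctance calls for a different approach to consent. A single ratio cannot tell these apart.

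**Working it through.** **Inputs.** The documents give 80 to be enrolled, the three routes, and the order of contact and screening. They give no accrual target, no expected percentage, no number to contact, and no eligibility or opt-in rate, so there is no planned figure to reproduce. As a consistency check, the enrolment table sums to 24 men + 56 women = 80, and 56/80 = 70%, which agrees with the text. All other inputs below are assumed.

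**1. What the single ratio leaves open.** Since enrolled ≤ eligible ≤ contacted,

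enrolled/contacted ≤ enrolled/eligible ≤ 100%.

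| Contacted (assumed) | Accrual | Possible enrolled/eligible |
|---|---|---|
| 160 | 80/160 = 50% | 50–100% |
| 240 | 80/240 = 33% | 33–100% |
| 400 | 80/400 = 20% | 20–100% |

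At 240 contacted, 33% fits both 80/100 = 80% and 80/200 = 40% of eligible people enrolling. This bound holds for any recruitment ratio in any trial, so it shows nothing particular to this one.

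**2. Route mix.** Take two routes with eligible shares e1 and e2, contact shares w and 1 − w, and 60% of eligible people enrolling on both:

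accrual = 0.6 × [w·e1 + (1 − w)·e2].

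Moving w from 0.25 to 0.75:

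- e1 = e2 = 40%: 24% and 24%
- 50% and 30%: 21% and 27%
- 60% and 20%: 18% and 30%

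Movement requires eligible shares to differ by route, and the documents do not say that they do. The Study Population sentence compares cancer sites, and both sites are recruited on every route.

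**3. Meaning of contacted, registry route only.** The ratio of the study-team reading to the registry reading is 1/(opt-in rate): 1/0.8 = 1.25 and 1/0.2 = 5.

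**4. Would enrolled over screened-and-eligible do better?**

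- People hear an overview before they are screened, so anyone declining at that point is never classified and leaves the new denominator. Take the case of 200 eligible with 80 enrolled (40%). If 100 of the 200 decline before screening, the ratio is 80/(200 − 100) = 80%, the same as the case it was meant to be told apart from.
- On the registry route, refusal can come at opt-in, before any screening by the study team.
- The pooled ratio also moves with route mix. Assume eligible shares of 30/20/60% and enrolment among eligible people of 40/60/70% (registry/clinic/individual). At a contact mix of 80/15/5, eligible = 0.24 + 0.03 + 0.03 = 0.30 and enrolled = 0.096 + 0.018 + 0.021 = 0.135. At 20/70/10, eligible = 0.06 + 0.14 + 0.06 = 0.26 and enrolled = 0.024 + 0.084 + 0.042 = 0.150. Enrolled/contacted goes from 13.5% to 15.0%; enrolled/eligible goes from 45.0% to 0.150/0.26 = 57.7%.
- Splitting 80 people by route gives imprecise figures. Wilson 95% intervals, (p + z²/2n ± z√[p(1 − p)/n + z²/4n²])/(1 + z²/n) with z = 1.96, are: 10/15 = 67% (42–85%), 20/30 = 67% (49–81%), 40/60 = 67% (54–77%).

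**The case for a change.** The strongest case for a change is that accrual is a headline feasibility outcome, its denominator is undefined on the registry route, and two analysts could both follow the SAP and report figures several-fold apart. The remedy is cheap: a sentence of definition and a tally by stage. It is also time-sensitive, because Safety Precautions says personal information on people who do not enrol will not be kept beyond study end.

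Part of this stands. The term is undefined in the text supplied, and a report that did not say where counting began would be hard to use. But the grant, the inclusion criteria table and the eligibility screener are attachments that are not shown, so a definition may exist there. The planned denominator already requires contacts to be counted before the lists go, and what is destroyed is identifying information; de-identified tallies are not barred. Every potential participant has a unique number whatever the route, which makes a stage table practicable.

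The part that does not stand is that one reading should be imposed. Starting the count at study-team contact would sit poorly with the recruitment section, which says the registry makes the initial contact. It would also remove registry non-responders and refusers from the denominator and so raise the figure. A second ratio would give only a partial separation of ineligibility from reluctance.

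**Conclusion.** No change to the plan is needed. Followed as written, item 1 yields a sound descriptive percentage: how many people enrol for each person contacted, which a later trial needs for planning contact volume. It feeds no test, threshold or sample size in the documents supplied. The undefined starting point is missing detail that an analyst would settle when counting, stating it by route. A recruitment-stage table is ordinary reporting that the SAP permits.

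The size in this trial cannot be derived. The bounds, the route-mix shifts and the 1.25- to 5-fold spread between readings all rest on assumed contact, eligibility, enrolment or opt-in figures; only the 80 enrolled is the plan's. Movement with route mix is a possibility, not something the documents show. Any enrolled-over-eligible figure an analyst adds should be read as conditional on opting in (registry route) and on agreeing to be screened. The conclusion assumes that no progression rule tied to the accrual percentage exists in the attachments not shown; such a rule would make the definition matter more.
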